8.5 Definition of end of trial

The expected duration of the study is 20 months from recruitment of the first participant. The end of the study is the date of the last follow up visit of the last participant.

9 Recording and reporting of adverse events

9.1 Unblinding

Not applicable as the study is an open uncontrolled feasibility study.

9.2 Notification of reportable protocol violations

A reportable protocol violation is a breach which is likely to effect to a significant degree:

(a) the safety or physical or mental integrity of the participants of the study; or

(b) the scientific value of the study.

The sponsor will be notified immediately of any case where the above definition applies during the study conduct phase. The Chief Investigator or designated individual will notify the sponsor of any protocol violation.

9.3 Trust incidents and near misses

An incident or near miss is any unintended or unexpected event that could have or did lead to harm, loss or damage that contains one or more of the following components:

- a. It is an accident or other incident which results in injury or ill health.
- b. It is contrary to specified or expected standard of patient care or service.
- c. It places patients, staff members, visitors, contractors or members of the public at unnecessary risk.
- d. It puts the Trust in an adverse position with potential loss of reputation.
- e. It puts Trust property or assets in an adverse position or at risk.

Incidents and near misses will be reported to the Trust through DATIX as soon as the individual becomes aware of them. A reportable incident is any unintended or unexpected event that could have or did lead to harm, loss or damage that contains one or more of the following components:

- a) It is an accident or other incident which results in injury or ill health.
- b) It is contrary to specified or expected standard of patient care or service.
- c) It places patients, staff members, visitors, contractors or members of the public at unnecessary risk.
- d) It puts the Trust in an adverse position with potential loss of reputation.
- e) It puts Trust property or assets in an adverse position or at risk of loss or damage.

10 Data management

10.1 Confidentiality

All data will be handled in accordance with the UK Data Protection Act 1998. The CRFs will not bear the participant's name or other personal identifiable data. The participant's initials, date of birth and study identification number, will be used for identification and this will be clearly explained to the patient in the Patient information sheet. Patient consent for this will be sought. All participant information will be stored in accordance with the UK Data protection Act 1998 guidance, with all personally identifiable information, stored in locked cabinets and stored separately from study data which will be pseudonymised and saved on password-protected computers at UCL. Each participant will be assigned an identification code, which will be used in all data storage, and will not contain any names or other personally identifiable information. After completion of the study all personal details will be deleted.

Participants will be assured that confidentiality will be kept unless there is evidence of risk of harm to self or others. This will be specified in the information sheet. If the screening assessment reveals undiagnosed disorders such as cognitive impairment suggestive of a neurodegenerative condition (identified from the Standardised Mini-Mental State Examination), or other undiagnosed psychiatric conditions (identified from the MINI International Neuropsychiatric Interview or Structured Clinical Interview for DSM-IV A xis II Disorders), then the participant's GP will be informed with their consent (or without their consent if there are concerns about risk of harm to self). Participants' GPs will also be informed of their participation in the study, with their consent.

10.2 Data collection tools and source document identification

Data will be collected from sites on study-specific CRFs or data collection tools such as electronic CRFs. Source data contained in source documents will be accurately transcribed onto the CRFs. Methods to maximise completeness of data will be applied when necessary. The Chief Investigator will have the primary responsibility of ensuring all data entered in the CRFs are accurate. A delegation log will identify all those personnel with responsibilities for data collection and handling, including those who have access to the trial database (Chief Investigator, Trial statistician, Research Assistant).

10.3 Completing Case Report Forms

All CRFs will be completed and signed by staff that are listed on the site staff delegation log and authorised by the Chief Investigator/Principal Investigator to perform this duty. The Chief Investigator will be responsible for the accuracy of all data reported in the CRF. In line with UCL's Data Protection Policy, trial documentation and anonymous data will be securely kept for a period of 10 years following completion of the study. All data from all sites taking part in this project will be kept and monitored at UCL. The Chief Investigator and or a designated individual will be responsible for any data queries.

10.4 Data handling

All data will be collected in accordance with the patient consent form, patient information sheet and section 8.4 of this protocol. UCL, as the study sponsor will act as the data controller for the study. All data will be handled in accordance with the UK Data Protection Act (1998). All data will be pseudo-anonymised using unique identification numbers and stored without contact details (names or addresses). Associations between participants' contact details and identification numbers will be stored in a separate encrypted electronic password-protected database. Access to this document will be restricted to the Chief Investigator and the research assistant. All data will be held on a secure database on a password-protected computer, and access to it will be restricted to the research team. Study consent forms will be kept in a locked cabinet at UCL for 10 years. Access to data will be uploaded to a secure server using a system called Data Safe Haven, which satisfies the highest level security requirements of NHS trusts. Treatment integrity ratings will be completed by an independent ACT therapist who will review audio files stored on the secure server using a UCL password protected computer. Transcriptions of qualitative interviews will be completed as soon as possible after collection and anonymised. Data will not be transferred to any party not identified in this protocol and will not to be processed and/or transferred other than in accordance with the patients' consent.

Quality control

Compliance to Good Clinical Practice (GCP) is now a requirement for all clinical trials. Accurate records will be kept, in line with the research protocol, in relation to recruitment, randomisation and data collection. Data will be collected and managed in a systematic way, and researchers will be trained, supervised and supported. Compliance to GCP, and quality control will be monitored in the beginning monthly and every three months subsequently. The Chief Investigator will ensure that all records are

maintained and participant confidentiality is assured. Quality control to a sample of data will be performed during the first weeks of data collection. Investigator Site Files and a Master file will also be kept that will source all documents of the study.

11 Statistical considerations

11.1 **Primary outcome**(s)

The indicators of success will be:

i) Acceptability:

a) Participants attending >=60% sessions;

b) 'Satisfactory' ratings of therapy, defined as a total score of 21 or more on the Satisfaction with Therapy and Therapist Scale-Revised (Oei et al., 2008).

ii) Feasibility:

a) Recruitment of $\geq 80\%$ of the target sample size in a 10 month recruitment period;

b) Retention rate of $\geq=60\%$ as measured by attendance at the final follow-up assessment.

Three out of four criteria will need to be met in order for success to be demonstrated.

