8.3 Subsequent assessments and procedures

This section describes all proposed outcome measures and assessments in Phase 2. Data collection will be conducted face-to-face (or via telephone at 20 weeks if face-to-face data collection is problematic).

Primary outcome measures

The co-primary outcome measures will be:

i) Acceptability:

a) Participants attending >=60% sessions;

b) 'Satisfactory' ratings of therapy using the Satisfaction with Therapy and Therapist Scale-Revised (Oei et al., 2008): A 12-item self-report measure of satisfaction with therapy and satisfaction with the therapist, rated on a 5-point scale from 1 (strongly disagree) to 5 (strongly agree). There is no set definition of what constitutes "satisfactory" and so we will define this as a total score of 21 or more on the Satisfaction with Therapy subscale.

ii) Feasibility:

a) Recruitment of $\geq 80\%$ of the target sample size in a 10 month recruitment period;

b) Retention rate of >=60%.

Secondary outcome measures

The secondary outcome measures will be:

i) Acceptability:

a) Failures to recruit due to lack of acceptability of the intervention;

b) Participants dropped out due to lack of acceptability of the intervention;

c) Credibility/Expectancy Questionnaire (Devilly et al., 2000): It is important to evaluate treatment credibility/expectancy when developing a new intervention as this can have a significant impact on uptake and dropout rates. The Credibility/Expectancy Questionnaire is a 6-item self-report measure that assesses the credibility of the rationale for therapy and treatment expectancy, which will be adapted for GAD and measured immediately after the first therapy session. Four items are rated on a 9-point scale from 1 to 9 (lower scores are worse) and 2 items are scored on an 11-point scale from 0 to 100%. As the measure includes items rated on two scales, the items will be standardised and summed to form separate composite scores for credibility and expectancy.

ii) Feasibility:

a) Eligible referrals overall and in each referral subgroup (self-referral, GPs, GP list searches, Improving Access to Psychological Therapies services, and Community Mental Health Teams);

b) Eligible participants recruited;

c) Failures to recruit for reasons other than dissatisfaction with therapy (together with reasons for this);

d) Participants dropped out for reasons other than dissatisfaction with therapy (together with reasons for this);

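### The co-primary satisfaction cut-off of 21 applies to the therapy subscale in Section 8.3 but to the whole 12-item scale in Section 11.1, where a respondent who leans towards disagreement on every item counts as satisfied

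*Protocol*

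**What the plan says.** Section 8.3 introduces its list with "The co-primary outcome measures will be" and places satisfaction with therapy among the acceptability measures. It describes the Satisfaction with Therapy and Therapist Scale-Revised (STTS-R) as "A 12-item self-report measure of satisfaction with therapy and satisfaction with the therapist", with each item scored from 1 (strong disagreement) to 5 (strong agreement). After noting that no established threshold exists, it chooses one: "we will define this as a total score of 21 or more on the Satisfaction with Therapy subscale".

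Section 11.1 lists the same outcome again as an indicator of success, this time "defined as a total score of 21 or more on the Satisfaction with Therapy and Therapist Scale-Revised". No subscale is named. The section then gives the decision rule: "Three out of four criteria will need to be met in order for success to be demonstrated". The other three criteria are session attendance, recruitment and retention.

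**The concern.** One number is applied to two different scores. A total of 21 can be a meaningful threshold on a subscale of about half the items, but on all 12 items it lies near the floor.

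The wording matters because Section 11.1 is where an analyst would look for the definition of a success criterion. Satisfaction is one of four criteria and one of only two that address acceptability. If nearly every respondent meets it, success in practice needs only two of attendance, recruitment and retention. The study could then be called a success with the attendance criterion failed and with a satisfaction criterion that could hardly have shown a problem, so with little informative evidence of acceptability. Assessing acceptability to inform a substantive trial is a stated objective (Section 4).

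If the discrepancy is left in place, someone must choose between the two definitions later. In an open, single-arm study that choice could be made after the scores are known.

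**Working it through.** **Inputs**

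- Number of items, whole scale: 12 (Section 8.3).
- Item scores: 1 to 5 (Section 8.3). Only the two end points are labelled, so 2 is taken as lying on the disagree side of the middle response, 3.
- Cut-off: 21 or more (Sections 8.3 and 11.1). Higher scores are taken as greater satisfaction, as a cut-off of this form implies.
- Number of items in the therapy subscale: not stated. Six is assumed (half of 12), with 5 and 7 shown as a range.

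The cut-off is set by definition, so there is no derivation to reproduce. What can be checked is where it falls on each score.

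**Formulas.** For *k* items scored 1 to 5, the range is *k* to 5*k*, the midpoint is 3*k*, the mean item score at the cut-off is 21/*k*, and a participant answering 2 throughout scores 2*k*.

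| Score used | *k* | Range | Midpoint | 21 per item | All answers 2 | Counted as satisfied? |
|---|---|---|---|---|---|---|
| Whole scale (11.1) | 12 | 12–60 | 36 | 1.75 | 24 | Yes |
| Subscale (8.3), assumed | 6 | 6–30 | 18 | 3.5 | 12 | No |
| Subscale, if shorter | 5 | 5–25 | 15 | 4.2 | 10 | No |
| Subscale, if longer | 7 | 7–35 | 21 | 3.0 | 14 | No |

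**Position on the whole scale.** (21 − 12)/(60 − 12) = 9/48 = 0.1875, so the cut-off sits about 19% of the way up the range. Nine answers of 2 and three of 1 are enough: 9 × 2 + 3 × 1 = 21. To fail, a respondent must average below 1.75 per item.

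**Size of the gap.** At the assumed subscale stringency of 3.5 per item, the matching whole-scale cut-off would be 12 × 3.5 = 42, twice the number printed.

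**Knock-on to other figures.** There is none. The two intervals in Section 11.3 reproduce as exact binomial limits and do not use the cut-off: 28/35 gives 0.631 to 0.916 (stated 0.63 to 0.92), and 40/60 gives 0.533 to 0.783 (stated 0.53 to 0.78).

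**The case against.** The strongest reply is that this is a dropped word and not a second definition. Section 8.3 gives the reasoned choice. Section 11.1 repeats the same number and still speaks of ratings of therapy. The Summary (Section 2) also describes the primary acceptability measure as satisfaction with therapy and does not mention the therapist. That reading is very likely right, and it supports the fix. It does not remove the error, because the faulty wording sits beside the success rule and nothing says that Section 8.3 takes precedence.

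A second reply is that the effect on the three-of-four rule cannot be stated exactly. Neither section says what proportion of participants must be satisfied, or out of which denominator. The schedule in Appendix 4 collects the STTS-R only at the follow-up visit, so non-attenders have no score. If all 40 participants formed the denominator, the most that could pass would be 35/40 = 87.5% at the planned follow-up, or 24/40 = 60% at the lowest acceptable retention. The criterion could then fail under the Section 11.1 wording for reasons unrelated to satisfaction. This stands: the claim that almost nobody can fail holds for people who complete the scale, and the claim about the study-level rule depends on the proportion and denominator chosen. Among completers, however, 21 out of 60 would satisfy almost any proportion.

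Third, the subscale length is assumed, so how strict Section 8.3 is cannot be settled: 21 is 4.2 per item with 5 items and 3.0 with 7. This also stands, but the contrast between the two sections survives across that range.

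Finally, the same 12 items are collected either way, both scores can be computed, and the primary analysis is descriptive. No data are lost. What is at risk is the pre-specification of a success criterion.

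**Conclusion.** The concern holds. Sections 8.3 and 11.1 define the same co-primary outcome incompatibly, and the Section 11.1 version is wrong as written. On a 12-to-60 scale it sets the bar at 1.75 per item, so a respondent scoring 24 by answering 2 throughout is classed as satisfied, while the subscale in Section 8.3 classes the same person as not satisfied.

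The mismatch and the whole-scale arithmetic rest only on figures printed in the protocol. The subscale comparison assumes 6 items and is unchanged for 5 to 7. The description of that respondent as dissatisfied assumes that 2 lies on the disagree side of 3. The weakening of the success rule applies among participants who complete the scale and cannot be given a precise size, because no required proportion is stated. Since this is a threshold in the decision rule, it should be corrected before any satisfaction scores are examined.

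**What to change.** In Section 11.1, state that the cut-off of 21 applies to the Satisfaction with Therapy subscale of the STTS-R, so that it matches Section 8.3. Beside it, give the number of items in that subscale and its possible range, so that the strictness of the threshold can be seen.

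The cost is one sentence. Data collection, the sample size and the intervals in Section 11.3 are unaffected. The criterion becomes harder to meet than Section 11.1 now implies, which is what Section 8.3 intended.

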11.2 Secondary outcome(s)

i) Acceptability:

a) Failures to recruit due to lack of acceptability of the intervention;

b) Participants dropped out due to lack of acceptability of the intervention;

c) Credibility/Expectancy Questionnaire (Devilly et al., 2000) after the 1st session of the intervention.

ii) Feasibility:

a) Eligible referrals overall and in each referral subgroup (self-referral, GPs, GP list searches, Improving Access to Psychological

Therapies services, and Community Mental Health Teams);

b) Eligible participants recruited;

c) Failures to recruit for reasons other than dissatisfaction with therapy (together with reasons for this);

d) Participants dropped out for reasons other than dissatisfaction with therapy (together with reasons for this);

e) Scores on the ACT Treatment Integrity Coding Manual (Plumb et al., 2010);

f) Deviations from the manual using the Adherence Checklist.

iii) Patient-reported outcome measures at 0 and 20 weeks:

a) Geriatric Anxiety Inventory (Pachana et al., 2007);

b) Penn State Worry Questionnaire (Meyer et al., 1990);

c) Geriatric Depression Scale-15 (Yesavage et al., 1983);

d) EQ-5D-5L including the VAS (EuroQol Group, 1990; Herdman et al., 2011);

e) A short modified version of the Client Service Receipt Inventory (Beecham et al., 1992; Serfaty et al., 2009);

f) Acceptance and Action Questionnaire-II (Bond et al., 2011).

11.3 Sample size calculation

The recruitment figure in Phase 1 is based on a sample size of 15 participants, consistent with the sample size recommended for qualitative interviews (Guest et al., 2006). The recruitment figure in Phase 2 is based on a sample size of 40 participants. A sample size of 35 is recommended in feasibility studies in order to provide sufficient data and precision of means and variances (Teare et al., 2014). Forty participants allows for a 12.5% loss to follow-up based on a preliminary study of ACT in older people with GAD (Wetherell et al., 2011a). With respect to session attendance, making the conservative assumption that 80% of participants in the feasibility study will attend 60% or more of sessions, a sample size of 35 (after loss to follow up) will give a 95% confidence interval of 0.63 to 0.92, indicating that we could be 95% certain that at least 63% of the target population will attend 60% or more of sessions was reported in 100% of older people with any form of GAD (i.e. not specifically treatment-resistant GAD; Wetherell et al., 2011a) and 78% of older people with depression (Karlin et al., 2013), a conservative estimate has been chosen given the target population. With respect to recruitment, making a conservative estimate that 60 participants will be eligible to participate in the feasibility study but only 40 will consent to participate, a sample size of 40 will give a 95% confidence interval of 0.53 to 0.78.

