8.4 Discontinuation/withdrawal of participants

In consenting to participate in the study, participants are consenting to intervention, assessments, follow-up and data collection. A participant may be withdrawn from the study whenever continued participation is no longer in the participant's best interests, but the reasons for doing so must be recorded (whenever possible). Reasons for discontinuing the study may include:

- active suicidal ideation with intent and plans;
- illness that may exclude the possibility of engagement in the intervention;
- a person withdrawing consent or losing the capacity to consent to participate in the study.

The decision to withdraw a participant from treatment will be recorded in the Case Report Form (CRF) and Investigator Site Files. If a participant explicitly states they do not wish to contribute further data to the study their decision must be respected and recorded in the CRF.

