11.5.2 Primary outcome analysis

In line with current recommendations of GCP in the analysis of feasibility studies, quantitative analyses will be descriptive. Binary and other categorical measures will be summarised using frequencies and percentages, and continuous measures using means and standard deviations (or medians and interquartile ranges for very skewed distributions). The precision of estimates will be assessed using 95% confidence intervals.

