Appendix 1 – Flowchart of phases in the FACTOID study.

Phase 1: Manual development	Conduct qualitative interviews with an estimated 15 older people with GAD. Discuss what components should be included in an intervention for older people with treatment-resistant GAD, and how it can be tailored to this population. Discuss with clinical experts in the field. Conduct nationwide online and paper-based survey of clinicians' and service users' views of what constitutes usual care for older people with treatment-resistant GAD. Develop and manualise an ACT intervention for older people with treatment-resistant GAD.
	Conduct qualitative interviews with the same 15 older people with GAD (as above) to discuss the acceptability of the intervention. Make modifications to it in collaboration with the Project Service User Advisory Group.
đị	Begin recruitment via self-referral and GP list searches and from GPs and Improving Access to Psychological Therapies services in primary care and Community Mental Health Teams for older people in secondary care.
llow.	
tion & fo	Identify and approach potential participants about the study ($n = 131$).
ıt, interver	Decline to participate (n = 46).
Inrolmer	Assess potential participants for eligibility ($n = 85$).
e 2: H	
Phas	Obtain consent to participate from eligible participants. Complete pre-intervention assessment (0 weeks; n = 40).
	Complete post-intervention assessment (20 weeks; n = 35). Conduct qualitative interviews with an estimated 15 older people and all therapists to further assess the acceptability of our manual.
ysis & ion	Complete data analysis (n = 40).
Analy	
Phase 3: . dissem	Make modifications to the manual in collaboration with the Project Service User Advisory Group. Write up and disseminate results.

Appendi x	2 –	Project	timetable	and	milestones
-----------	-----	---------	-----------	-----	------------

Date	Activity	Milestone(s)
Months -6-0: Nov	Pre-orientation	Apply for ethical and research governance approvals. Place advert for research
2016-Apr 2017		assistant with date of interview. Devise 4-day training workshop. Identify
		therapists.
Months 1-3: May-	Orientation & Phase	Interview and appoint research assistant. Purchase equipment. Develop procedures
Jul 2017	1: Develop manual	and policies for the conduct of the study. Set up Project Development Group,
		Project Management Group and Study Steering Committee. Conduct first wave of

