Appendix 4 – Schedule of assessments

	Phase 1: Screening	Phase 1 develo	: Manual pment	Phase 2: Screening & baseline Ax		Phase 2: Intervention						Phase 2: Follow-up Ax	
Visit No	1	2	3	1	2-3	4-5	6-7	8-9	10-11	12-13	14-15	16-17	18
Day(s)	1	2	3	1	1-2	3-4	5-6	7-8	9-10	11-12	13-14	15-16	1
Window of flexibility for visits	N/A	e.g. +/- 2 weeks	e.g. +/- 2 weeks	N/A	e.g. +/- 2 weeks	e.g. +/- 2 weeks	e.g. +/- 2 weeks	e.g. +/- 2 weeks	e.g. +/- 2 weeks	e.g. +/- 2 weeks	e.g. +/- 2 weeks	e.g. +/- 2 weeks	e.g. +/- 2 weeks
Informed consent	Х			Х									
GAD-7	Х			Х									
MINI	Х			Х									
SCID	Х			Х									
SMMSE	Х			Х									
Eligibility confirmation	Х			Х									
GAI				Х									Х
PWSQ				Х									Х
GDS-15				Х									Х
EQ-5D-5L				Х									Х
CSRI				Х									Х
AAQ-II				Х									Х
STTS-R													Х
CEQ					Х								
Qualitative interview		Х	Х										Х
Intervention					ACT+	ACT+	ACT+	ACT+	ACT+	ACT+	ACT+	ACT+	
AE review	X			X	Х	Х	Х	Х	Х	Х	Х	Х	X

Note: AAQ-II = Acceptance and Action Questionnaire-II; ACT+ = Acceptance and Commitment Therapy plus usual care; AE = adverse events; Ax = assessment; CEQ = Credibility/Expectancy Questionnaire; CSRI = Client Service Receipt Inventory; GAD-7 = Generalized Anxiety Disorder-7; GAI = Geriatric Anxiety Inventory; GDS-15 = Geriatric Depression Scale-15; MINI = MINI International Neuropsychiatric Interview; PSWQ = Penn State Worry Questionnaire; SCID = Structured Clinical Interview for DSM-IV Axis II Disorders; SMMSE = Standardised Mini-Mental State Examination; STTS-R = Satisfaction with Therapy and Therapist Scale-Revised.

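### Attendance precision is planned on 35 people though all 40 can be counted, and satisfaction is collected only from those who reach the 20-week visit

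*Protocol*

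**What the plan says.** Section 11.3 sets the Phase 2 size: "The recruitment figure in Phase 2 is based on a sample size of 40 participants". It continues: "Forty participants allows for a 12.5% loss to follow-up", which leaves 35. For session attendance it proceeds by "making the conservative assumption that 80% of participants in the feasibility study will attend 60% or more of sessions", and concludes that "a sample size of 35 (after loss to follow up) will give a 95% confidence interval of 0.63 to 0.92". From the lower limit it infers, with 95% certainty, that at least 63% of the target population will attend enough sessions.

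Sections 8.3 and 11.1 list four criteria: attendance at 60% or more of sessions, a satisfaction score of at least 21, recruitment of at least 80% of target, and retention of at least 60%. Section 11.1 measures retention by attendance at the final follow-up and requires three of the four for success. Neither section gives a denominator for the two acceptability criteria. Section 11.5.2 adds only that the analysis is descriptive and that "The precision of estimates will be assessed using 95% confidence intervals".

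Appendix 1 shows "Complete post-intervention assessment (20 weeks; n = 35" and then gives 40 for data analysis. In Appendix 4 ("STTS-R = Satisfaction with Therapy and Therapist Scale-Revised"), the STTS-R row has a single mark, in the follow-up column at visit 18.

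**The concern.** There are two separate problems.

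- **Attendance.** It is a count of sessions. Therapists complete a checklist at each session (section 8.2.1), and the costing uses sessions attended per participant (section 11.5.6). Someone who never returns at 20 weeks still has a known attendance figure, so removing expected losses to follow-up from this calculation is unnecessary. It also sits badly with the 40 in Appendix 1. Read literally, the inference about the target population would hold only for people who return.
- **Satisfaction.** A participant who misses visit 18 has no score, and no analysis plan can recover a score that was never collected. People who stop therapy because they dislike it are plausibly both less likely to return and less likely to rate it well.

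Both criteria feed the three-of-four rule. Under that rule success can be declared even when retention fails, in which case satisfaction would rest on fewer still.

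**Working it through.** **Inputs.** Enrolled n = 40, loss 12.5%, assumed attendance proportion 80% (section 11.3); retention criterion 60% (section 11.1); STTS-R at visit 18 only (Appendix 4).

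**Formula.** Exact (Clopper-Pearson) 95% interval for x of n: lower = Beta quantile 0.025 with parameters (x, n − x + 1); upper = Beta quantile 0.975 with parameters (x + 1, n − x).

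**Step 1: reproduce the plan's figure.** 40 × (1 − 0.125) = 35, and 0.80 × 35 = 28. The exact interval for 28/35 is 0.631 to 0.916, which matches the stated 0.63 to 0.92. The same method reproduces the stated recruitment interval: 40/60 gives 0.533 to 0.783. The arithmetic in section 11.3 is correct.

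**Step 2: the same assumption on all enrolled.** 0.80 × 40 = 32. The exact interval for 32/40 is 0.644 to 0.909, or 0.64 to 0.91.

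**Step 3: how much the denominator could matter for attendance.** Suppose 28 of 35 returners attend enough sessions, and k of the 5 lost also do. The figure over all enrolled is (28 + k)/40.

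| k | Proportion | Exact 95% CI |
|---|---|---|
| 0 | 28/40 = 70% | 0.53 to 0.83 |
| 3 | 31/40 = 77.5% | 0.615 to 0.892 |
| 5 | 33/40 = 82.5% | 0.672 to 0.927 |

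The range is 70% to 82.5%, against 80% among returners. This illustrates sensitivity to the denominator; it does not describe an analysis that the protocol has specified.

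**Step 4: satisfaction.** With r rated and s satisfied, the figure among those rated is s/r. Over all 40 it lies between s/40 (nobody unrated satisfied) and (s + 40 − r)/40 (everybody unrated satisfied). The retention criterion is met at r = 0.60 × 40 = 24. Taking s = 20 as an assumed example:

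- among those rated: 20/24 = 83% (0.626 to 0.953);
- lower bound: 20/40 = 50% (0.338 to 0.662);
- upper bound: (20 + 16)/40 = 36/40 = 90%.

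At the retention limit, the 16 unrated people leave a band of 40 percentage points. At the planned retention of 35, with 28 satisfied as an example, the band is 28/40 = 70% to 33/40 = 82.5%.

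**The case against.** **Section 11.3 is a planning calculation, for attendance only.** It fixes no analysis set, and the only number attached to analysis is the 40 in Appendix 1. This stands. A reader might infer from the 35 that the attendance analysis leaves out people who dropped out; the protocol does not establish that. It shows an unnecessary planning denominator that disagrees with another section.

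**The numerical correction for attendance is trivial.** Moving from 0.63–0.92 to 0.64–0.91 shifts each limit by about 0.01. This also stands. The 80% is assumed for participants in the study, not for returners, so 28/40 is a scenario and not an error exposed.

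**No threshold is crossed.** A reader might take a lower limit under 60% as failing a protocol bar. There is no such bar: 60% is the share of sessions a person attends and, separately, the retention rate. No required proportion of participants is stated for attendance or for satisfaction.

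**Section 8.4 does not make leaving therapy equal to leaving the study.** The reason listed is "illness that may exclude the possibility of engagement in the intervention", which concerns illness. The section also mentions withdrawal from treatment separately from a refusal to contribute further data. Stopping ACT and missing week 20 are different events. Section 8.4 does not, however, say that the 20-week assessment is still sought from someone who stops ACT.

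**Drop-out is already visible.** Retention is its own criterion, drop-out for lack of acceptability is a secondary outcome, missing values will be reported, and section 8.3 allows telephone collection at 20 weeks. All of this mitigates. None of it supplies a satisfaction rating for a person who is not assessed at 20 weeks, and the secondary outcome does not enter the three-of-four rule.

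**Denominators and missing-data rules can sit in the SAP.** That is fair for the denominators. It does not answer the schedule, which determines what is collected.

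**Conclusion.** The point holds in two parts of unequal weight. The 35 in section 11.3 should be aligned with the 40 in Appendix 1; the effect on the planned interval is about 0.01 at each limit. The weightier part is the schedule: one of the four success criteria is observed only in people assessed at 20 weeks.

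Overstated satisfaction is likely but not certain. It rests on the assumption that people who are not retained would have rated therapy less favourably, which the documents neither show nor exclude. Without ratings from them, the uncertainty is the band in step 4: 50% to 90% at 24 rated with 20 satisfied, and 70% to 82.5% at 35 rated with 28 satisfied. This merits a change before data collection, because it cannot be repaired afterwards.

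**What to change.** 1. In sections 8.3 and 11.1, state all enrolled participants as the denominator for attendance. In section 11.3, restate the interval as 32/40, exact 95% CI 0.64 to 0.91, so that it agrees with Appendix 1.
2. In Appendix 4, add the STTS-R by post or telephone at the point where a participant stops ACT.
3. In section 8.4, state that the 20-week assessment is still sought from participants who stop ACT unless they withdraw consent to data collection.
4. Report satisfaction among those rated, together with the number unrated. As a sensitivity bound, report it among all 40 with unrated people counted as not satisfactory. This should not be the sole definition: it would code people lost through illness or loss of capacity as dissatisfied, and would tie satisfaction mechanically to retention.

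The cost is protocol wording, a 12-item form sent to a few people, and a possibly lower satisfaction figure.
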